7.4. Postoperative Follow-up Evaluations

Subjects will be seen at the 3 months, 1 year, 3 years, 5 years, 7 years and 10 years interval post surgery. The Harris Hip Score will be collected and the HOOS and UCLA questionnaire obtained at each visit.

Anteroposterior (AP) and (shoot trough) lateral radiographs of the operated hip will be taken before discharge in addition to at 1 year, 3 years, 5 years, 7 years and 10 years postoperatively. At least the 1 year follow-up radiograph should include full pelvic overview (including at least 20 cm of the proximal femur). Pelvic AP radiograph will be used for analysis of cup inclination and leg length discrepancy.

Postoperative radiographs will be taken to determine component alignment, radiolucencies^{20,21}, and bone condition. The alignment of the femoral prosthesis will be measured as the angle between the central axes of the proximal femoral canal and the femoral prosthesis. Angles will be classified as varus, valgus or neutral²². The angle of the acetabular cup will be

assessed by measuring the angle of vertical tilt of the acetabular cup (angle between a line joining the ischial tuberosities and one through the long axis of the ellipse of the acetabular cup)²³. Additionally, the cup anteversion will be recorded. Observations will be recorded on the x-ray case report form and independently reviewed.

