7.2 Analysis Populations

The following are the analysis populations used in summarizing all tables:

Safety Analysis Population (SAF)

This will include all subjects (Hips) enrolled and implanted with the study device in the study.

Full Analysis Set (FAS)

The FAS population will include all subjects (Hips) in the SAF with at least one postoperative assessment on any of the Patient Reported Outcome Measures (PROMs).

Per Protocol (PP) Population

The PP population will include all subjects (Hips) in FAS, who have no significant protocol deviations and satisfy all study eligibility criteria and the inclusion/exclusion criteria. Significant protocol deviations leading to removal from the PP population will be determined and finalized prior to the final analyses at 10 years. The final assignment of a subject to the PP population will be established after all protocol deviations have been reviewed and evaluated. Subjects excluded from the PP will be documented/listed together with their reason(s) for exclusion.

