7.9 Analysis of Primary Endpoint

The Kaplan-Meier survival estimate would be used to estimate implant survivorship. Time to device revision will be the endpoint of interest to estimate the implant survivorship. Implant survival time (in months) is computed as: (Event Date – Operative Date+1)/30.4375.

Implanted hips that continue until study completion without an on-study revision will be censored at their last known date of participation in the study. Any premature hip discontinuation from study due to a subject's death or any other reason will be censored on the date of this discontinuation. A subject who is lost to follow-up will be censored at the subject's last known contact date. The Cumulative proportion of implant survivorship at 36 months (3-year), 60 months (5 years), 84 months (7 years) and 120 months (10 years) will be estimated and displayed accordingly. These Kaplan-Meier estimates will be provided with their corresponding two-sided 95% Confidence Intervals (CIs). If feasible, Kaplan-Meier survival graphs will be displayed to graphically illustrate implant survivorship over the study duration.

For the a-priori protocol-specified hypothesis, if the lower bound of 95% two-sided CIs at 3 years, 5 years, 7 years and 10 years are not less than 97%, 95%, 93% and 90% respectively, then we conclude that implant survivorship of the R3 cup is at least 97% at 3 years, 95% at 5 years, 93% at 7 years, and 90% at 10 years follow-up respectively.

The primary endpoint analysis will be performed on the FAS population. As sensitivity analysis, the same analysis will be performed on the PP population.

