7.12 Additional Analysis

Type of R3 bearing would be classified into meaningful subgroups by the Clinical Strategy team using Head/Inlay/Inlay Material available in the database. Implant survivorship would subsequently be summarized exploratorily for each of the classified subgroup of the R3 bearing (head/inlay: i.e. Biolox delta ceramic-on-ceramic, Biolox forte ceramic-on-ceramic, Oxidized zirconium-on-

CONFIDENTIAL AND PROPRIETARY

This document contains information that is confidential and proprietary to Smith & Nephew PLC and Smith & Nephew, Inc. and is intended for use only by Smith+Nephew and its manufacturer. It shall not be reproduced or copied in whole or in part, nor shall the contents be disclosed by any means without prior written permission from Smith+Nephew, nor shall anyone make any use of it that is contrary to the expressed or implied wishes of Smith+Nephew.

Statistical Analysis Plan

A prospective, multicenter, non-randomized, clinical outcomes study of the R3[◊] Acetabular System in patients with degenerative hip disease

Number:
R3H01/02/01/2017
ST: 1103
Version: 3.0
Page: 17 of 18

crosslinked polyethylene, Ceramic-on-crosslinked polyethylene, Metal-on-crosslinked polyethylene and Metal-on-metal) using Kaplan-Meier survival methods as described in Section 7.9.

The analysis population for these analyses would be the FAS population.

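### The primary survivorship analysis is restricted to hips with a postoperative PROM, so a known early revision can drop out of the estimate and its 97/95/93/90% rule

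*SAP*

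**What the plan says.** - **Endpoint.** SAP 7.9: "Time to device revision will be the endpoint of interest to estimate the implant survivorship". Time runs from the operative date.
- **Decision rule.** SAP 7.9 sets thresholds of 97/95/93/90% at 3/5/7/10 years. Each claim is made "if the lower bound of 95% two-sided CIs at 3 years, 5 years, 7 years and 10 years are not less than" its threshold.
- **Population.** SAP 7.9: "The primary endpoint analysis will be performed on the FAS population". SAP 7.2 defines the FAS as "all subjects (Hips) in the SAF with at least one postoperative assessment on any of the Patient Reported Outcome Measures".
- **The wider set.** SAP 7.2 also defines the SAF, with no PROM condition: "This will include all subjects (Hips) enrolled and implanted with the study device in the study".
- **Sensitivity and subgroups.** The only sensitivity analysis of the primary endpoint uses the PP set, and SAP 7.2 says "The PP population will include all subjects (Hips) in FAS". For survivorship by bearing type, SAP 7.12 says "The analysis population for these analyses would be the FAS population".
- **Visit timing.** Protocol 7.4: "Subjects will be seen at the 3 months, 1 year, 3 years, 5 years, 7 years and 10 years interval post surgery". Harris Hip Score, HOOS and UCLA are not scheduled at operation or discharge (Protocol 7.1, Table 1).
- **Revision capture.** Protocol 8 records adverse events from implantation onward, and Protocol 8.1 D puts every revision on the Adverse Event CRF.
- **Protocol basis.** Protocol 5.3 and 9 specify intention-to-treat. SAP 7.14 lists the FAS as the primary population without giving a reason.

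**The concern.** A time-to-revision analysis needs an implant date and either a revision date or a last-contact date. A PROM adds nothing to it. Making a PROM a condition of entry selects hips on something that happens after surgery and that an early failure can prevent. A hip revised before 3 months with no PROM at any later visit leaves both the event count and the denominator, although its failure is in the database.

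The expected bias from such exclusions is upward, both in the estimate and in the lower bound that alone decides the four claims. Protocol 8.3 itself anticipates short-term explantation for infection, instability or pain, so such hips are plausible.

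Nothing planned corrects the estimate. The PP set and the bearing subgroups lie inside the FAS. The revision listing (SAP 5.3), hip accountability (SAP 7.6) and adverse event tables (SAP 7.11) would disclose these hips but do not feed the Kaplan-Meier curve.

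**Working it through.** The plan gives no calculation to reproduce. The target of 500 rests on the ODEP minimum cohort (SAP 6.1), with no assumed survivorship, power or interval width.

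**Inputs from the documents:** 512 enrolled (SAP 6.1); thresholds S0 = 97/95/93/90% and two-sided 95% intervals (SAP 7.9).

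**Assumptions:** one hip per subject; no censoring unless stated; one excluded revision. The SAP names no interval type, so log-log is used, with linear shown for comparison.

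**Formulas.** Without censoring, S = 1 − x/n and the Greenwood SE = √(S(1−S)/n). The log-log lower bound is S^exp(1.96σ), with σ = SE/(S·|ln S|).

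**Step 1: revisions the rule tolerates, n = 512.** The largest x whose lower bound reaches the threshold is 7/15/24/37 (log-log) or 9/17/26/39 (linear) at 3/5/7/10 years.

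**Step 2: drop one revision when the count is one above the log-log limit.** Worked at 3 years:
- All implanted hips, 8/512: S = 0.98438, SE = 0.00548, σ = 0.3536, exp(1.96σ) = 2.000. Lower bound 96.90%, fails.
- FAS, 7/511: S = 0.98630, SE = 0.00514, σ = 0.3780, exp(1.96σ) = 2.098. Lower bound 97.15%, passes.

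| Year | All implanted | Lower bound | FAS | Lower bound | Rise in S (points) |
|---|---|---|---|---|---|
| 3 | 8/512 | 96.90% | 7/511 | 97.15% | 0.193 |
| 5 | 16/512 | 94.95% | 15/511 | 95.18% | 0.190 |
| 7 | 25/512 | 92.86% | 24/511 | 93.07% | 0.186 |
| 10 | 38/512 | 89.94% | 37/511 | 90.15% | 0.181 |

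**Step 3: false-claim rate when true survivorship equals S0.** Let X ~ Binomial(512, 1−S0) and L be the log-log limit. With no exclusion the rate is P(X ≤ L). With one revision excluded, the limit at n = 511 is still L, so the rate is P(X ≤ L+1). The increase is P(X = L+1).

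| Year | None excluded | P(X = L+1) | One excluded |
|---|---|---|---|
| 3 | 1.36% | 1.57% | 2.92% |
| 5 | 1.50% | 1.15% | 2.65% |
| 7 | 2.02% | 1.15% | 3.17% |
| 10 | 1.84% | 0.86% | 2.70% |

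The nominal one-sided rate is 2.5%. Linear intervals exceed it with nothing excluded. That is a question of interval type and is not counted here.

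**Step 4: the opposing effect.** The FAS also drops unrevised hips with no PROM, which lowers the estimate. Start from x = L+1 with one revision excluded. The smallest number m of event-free hips, each followed to the time point, that cancels the rise satisfies (x−1)/(511−m) ≥ x/512. This gives m = 63/31/20/13. To bring the log-log lower bound back below the threshold takes 26/19/6/8. If the unrevised hips are lost early they hardly count: with 20 censored at 3 months and dropped, one revision at month 1 excluded and the other revisions evenly spaced from month 4, the net rise is still 0.193/0.189/0.186/0.181 points.

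**Step 5: censoring.** This used 10,000 simulated cohorts with exponential revision and censoring times, the earliest revision removed, and log-log intervals. False-claim rates, none to one excluded:
- 15% censored by 10 years: 1.5 to 3.6, 1.7 to 2.6, 1.9 to 2.7 and 2.0 to 2.6% at 3/5/7/10 years.
- 30% censored: 1.5 to 2.9, 1.5 to 2.6, 2.1 to 2.9 and 2.0 to 2.7%.

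**The case against.** The strongest reply is that no affected hip has been shown. Exclusion requires a revision and no PROM on any instrument at any of six visits over ten years. An early-revised hip with one later PROM stays in and is counted. The main protocol does not end follow-up at revision. That rule appears only in section 7.2 of the post-approval addendum, which covers subjects already past 3 years. At 10 years, the time point of the primary endpoint, one exclusion is worth 0.18 points and reverses the claim only at exactly 38 revisions. The choice of interval type alone matters more. The error rates assume true survivorship exactly at the threshold, while the only survivorship figure in the documents is 99.3% at 3 years, in one bearing cohort of 137. Unrevised hips without a PROM pull the other way. Revisions will be listed in any case. A SAF sensitivity analysis would expose any difference without changing the primary population after the last subject's last visit.

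Most of this stands as a statement about size: the count is unknown and possibly zero, and the error rates are conditional. It does not make the rule sound. Disclosure in a listing leaves the estimate uncorrected, and a SAF sensitivity analysis would leave the deciding bound on the set that can omit failures. The SAF is not strictly intention-to-treat, since Protocol 5.3 counts subjects from consent. It is the closest available set, because a hip never implanted has no survival time.

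**Conclusion.** The concern holds and must be fixed. As written, the SAP makes entry to the primary device-failure analysis depend on a postoperative assessment that failure can pre-empt, and no planned analysis restores the lost events.

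Under the working assumptions the size is modest: 0.18 to 0.19 points per excluded revision, and false-claim rates that pass 2.5% at all four times (2.65 to 3.17%). The 3-year claim tolerates the fewest revisions, seven. If every revised hip has a PROM, the upward bias is zero. Confidence is high on the reading of the text. The number of affected hips cannot be known from the documents, and the severity rests on the primary rule being unprotected, not on a demonstrated count.

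**What to change.** - In SAP 7.9 and 7.12, run the Kaplan-Meier analysis and the decision rule on the SAF: all implanted hips, with time zero at surgery.
- Keep the FAS for the PROM endpoints.
- Define the PP set for survivorship from the SAF, without the PROM condition.
- Report FAS survivorship as a sensitivity analysis, with the number of SAF hips, and of revisions, that fall outside the FAS.
- In SAP 7.14, record the change, its reason (the protocol's intention-to-treat basis) and whether results had been seen when it was made.

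**Cost.** This is a late amendment to a SAP already at version 3.0, after the last subject's last visit, so the statement on timing matters. It needs no new data, only a population flag and rerun survivorship tables. The estimate may become slightly less favourable.

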7.3 Handling of Missing, Incomplete and Repeat Data

For the primary endpoint, subjects with hips that are prematurely discontinued from the study due to death or loss to follow-up would be censored on the last known date on-study.

Specific instructions for handling missing PROMs is described in Section 7.4. If $\geq 10\%$ of postoperative UCLA, HOOS or HHS scores at more than 2 of the postoperative follow-up time points are missing, only their observed data will be summarized using the change from preoperative to each postoperative time point as the endpoints of interest.

CONFIDENTIAL AND PROPRIETARY

This document contains information that is confidential and proprietary to Smith & Nephew PLC and Smith & Nephew, Inc. and is intended for use only by Smith+Nephew and its manufacturer. It shall not be reproduced or copied in whole or in part, nor shall the contents be disclosed by any means without prior written permission from Smith+Nephew, nor shall anyone make any use of it that is contrary to the expressed or implied wishes of Smith+Nephew.

Statistical Analysis Plan

A prospective, multicenter, non-randomized, clinical outcomes study of the R3[◊] Acetabular System in patients with degenerative hip disease

Number:
R3H01/02/01/2017
ST: 1103
Version: 3.0
Page: 10 of 18

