5.5. Subject Withdrawal / Termination Criteria

Whilst subjects are free to withdraw from the study at any time. All reasonable efforts should be made to retain the subjects for the 10-year duration of this study.

Study Site Discontinuation

A specific study site in this multicenter study may also warrant termination under the following conditions:

- non-compliance to Good Clinical Practice (GCP) or protocol
- major protocol deviations
- inaccurate or incomplete data
- unsafe or unethical practices
- safety or performance considerations
- investigator involuntarily discontinues participation in study

Documentation of withdrawn and lost to follow-up patients

Some actively enrolled subjects will not return for follow-up exams due to a variety of reasons. Study personnel will make all reasonable efforts to contact the subject and document the following contact attempts prior to declaring a subject to be lost to follow-up: the subject has been contacted according to the study sites policies, but no less than 2 documented phone contacts attempts and 1 letter without response. Copies of all attempts to reach the subjects per regular mail or email and/or the attempts to contact the subject via other means should be documented and kept with the subjects Case Report Form (CRF). A subject will be considered lost to follow-up if he/she does not appear for the scheduled study visit for 2 consecutive visits and study personnel are unable to contact the subject. For all cases (withdrawn and lost to follow-up), information will be obtained on the Study Termination Form, detailing circumstances leading to the withdrawal.

Sites will be requested to contact non-respondent patients using phone calls, regular mail, e-mail, certified letters or other means to urge patients to return to a clinic for follow-up or ascertain if a patient has moved.

6. Medical Devices

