6 STATISTICAL CONSIDERATIONS

6.1 Determination of Sample Size

The target enrollment during this study was 500 patients however 512 subjects have been enrolled. This number of patients leads to representative results with a greater precision of the survival rates, i.e. small confidence intervals.

The sample size is large enough to satisfy pseudo-regulatory requirements set-forth in individual European countries such as the Orthopaedic Data Evaluation Panel¹ (ODEP) and the National Institute for Clinical Excellence (NICE) requirements². According to the ODEP criteria for categorizing products in relation to NICE's long-term benchmarks for hip replacements, a level A study (strongest evidence) requires an initial cohort of 500 patients or more.

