7 STATISTICAL ANALYSIS

7.1 General

Smith+Nephew's Global Biostatistics group will conduct the statistical analysis for this study. Unless otherwise stated, all significance tests and hypothesis testing will be two-sided, performed at the 5% significance level. Resulting p-values will be quoted and 95% two-sided confidence intervals will be generated where appropriate. All p-values will be rounded to three decimal places, p-values less than 0.001 will be presented as '<0.001' in all tables.

CONFIDENTIAL AND PROPRIETARY

This document contains information that is confidential and proprietary to Smith & Nephew PLC and Smith & Nephew, Inc. and is intended for use only by Smith+Nephew and its manufacturer. It shall not be reproduced or copied in whole or in part, nor shall the contents be disclosed by any means without prior written permission from Smith+Nephew, nor shall anyone make any use of it that is contrary to the expressed or implied wishes of Smith+Nephew.

Statistical Analysis Plan

A prospective, multicenter, non-randomized, clinical outcomes study of the R3[◊] Acetabular System in patients with degenerative hip disease

Number:
R3H01/02/01/2017
ST: 1103
Version: 3.0
Page: 9 of 18

Where data summaries are specified, categorical and ordinal variables will be summarized with frequencies and percentages. Continuous variables will be summarized with the following summary statistics: number of observations, mean, median, standard deviation, minimum and maximum values. All analyses will be performed in SAS 9.4 (or later).

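### The 10-year claim assumes lost hips are later revised at the same rate as followed hips, no planned analysis tests this, and a narrow pass (about 93–93.5%) would be fragile to it

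*SAP*

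**What the plan says.** SAP 7.9 names the estimator: "The Kaplan-Meier survival estimate would be used to estimate implant survivorship". The claim is made at 3, 5, 7 and 10 years if the lower bounds of the two-sided 95% intervals "are not less than 97%, 95%, 93% and 90% respectively". The type of interval is not named.

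SAP 7.3 has hips that end early through death or loss "censored on the last known date on-study". SAP 7.9 repeats this ("A subject who is lost to follow-up will be censored", at last known contact) and also censors discontinuation for any other reason at its date.

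The primary analysis uses the FAS. On robustness SAP 7.9 says only: "As sensitivity analysis, the same analysis will be performed on the PP population". SAP 7.2 defines the PP population as a subset of the FAS. SAP 7.12 adds exploratory bearing subgroups by the same Kaplan-Meier method.

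Protocol 5.5 defines loss: "A subject will be considered lost to follow-up if he/she does not appear for the scheduled study visit for 2 consecutive visits", and in addition the site cannot reach the subject, after at least two documented phone attempts and one letter.

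**The concern.** Kaplan-Meier with censoring at loss is valid when a hip's later revision risk is unrelated to its being lost. That is open to doubt here. After year 1 the visits are at 3, 5, 7 and 10 years, so a hip last seen at year 3 or 5 can have 5 to 7 unobserved years before the primary time point. A patient who is unhappy with the hip, or was revised elsewhere, is a plausible non-attender. If lost hips are revised more often, survivorship is biased upward, and loss accumulates towards year 10.

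The PP rerun keeps the same assumption. It may even look reassuring for the wrong reason: Protocol section 12 counts missed visits as deviations, so if these are judged significant, PP drops poorly followed hips. Agreement between FAS and PP would say nothing about what happened to the hips that were lost.

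Protocol section 9 promises multiple imputation for missing data. The SAP does not carry it to the primary endpoint, and SAP 7.14 does not list the change. That imputation was justified under missing at random, so it would not by itself have tested the assumption either.

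**Working it through.** The documents give no expected survivorship, event count, power or loss rate for the 10-year claim, so there is no planned figure to reproduce. The check asks how much worse lost hips must do before the claim fails.

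**Inputs from the documents**
- 95% two-sided interval (SAP 7.1: "two-sided, performed at the 5% significance level"), z = 1.96.
- 10-year threshold 90% (SAP 7.9).
- N = 512 (SAP 6.1: "512 subjects have been enrolled").

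**Assumptions**
- All 512 are in the FAS as independent hips.
- Constant revision hazard.
- A fraction L = 10%, 20% or 30% is lost evenly over 10 years.
- The interval is either linear or log-log.

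**Formulas**, with S the observed 10-year estimate, Λ = −ln S and x the fraction of the 10 years elapsed:
1. Greenwood variance of Λ: (Λ/N) × ∫₀¹ e^(Λx)/(1 − Lx) dx.
2. Lower limit: linear S(1 − z·SE); log-log exp(−Λ·e^(z·SE/Λ)).
3. If lost hips have hazard k times as high after loss: S_k = (1 − L)S + L(S − S^k)/((k − 1)Λ). The relative SE of the cumulative hazard is held fixed and step 2 is repeated.

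**Worked case: S = 93%, L = 20%**
- Λ = 0.0726. The integral is about 1.16, so SE = √(0.0726/512 × 1.16) = 0.0128, and SE/Λ = 0.177.
- As the SAP plans it (k = 1): linear 0.93 − 1.96 × 0.93 × 0.0128 = 90.7%; log-log exp(−0.0726 × e^0.346) = 90.25%. Both pass.
- With k = 2: S₂ = 0.8 × 0.93 + 0.2 × (0.93 − 0.8649)/0.0726 = 92.3%, that is 512 × (0.9300 − 0.9234) = 3.4 extra revisions. The new Λ is 0.0797. Lower limits: linear 89.8%, log-log 89.35%. Both fail.

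The smallest estimate that passes is 92.4% (linear) or 92.7% (log-log) with 10% lost, and 92.5% or 92.9% with 30% lost.

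**Multiplier k at which the lower limit falls below 90% (log-log to linear)**

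| Observed 10-year estimate | 10% lost | 20% lost | 30% lost | Extra revisions, 20% lost |
|---|---|---|---|---|
| 93.0% | 1.8–2.7 | 1.3–1.8 | 1.1–1.4 | 0.9–2.6 |
| 93.5% | 3.2–4.4 | 2.0–2.5 | 1.6–1.9 | 3.0–4.8 |
| 94% | 5.0–6.4 | 2.8–3.5 | 2.1–2.5 | 5.1–6.9 |
| 95% | 9.7–12 | 4.9–5.8 | 3.4–4.0 | 9.0–11.1 |

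For the point estimate itself to fall from 93.0% to below 90%, k must reach 12.5, 6.0 or 4.2 at 10%, 20% or 30% lost.

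**Cross-check by multiple imputation.** Eight simulated datasets with an observed 94% and 30% lost (log-log pooling) tipped between k = 2 and 2.5 in seven cases and between 1.5 and 2 in one, close to the formula's 2.1.

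**False claims.** If true 10-year survivorship is exactly 90%, simulation (4,000 trials per cell) gives these chances of declaring success, log-log to linear:

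| Lost | k = 1 | k = 2 | k = 3 |
|---|---|---|---|
| 20% | 2.0–3.6% | 6.5–11.5% | 17.0–25.5% |
| 30% | 2.2–4.1% | 11.5–18.8% | 28.4–40.2% |

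**The case against.** The plan has real safeguards:
- A missed visit is not a missing endpoint. Protocol 7.5 allows a telephone call asking whether the device is still in place.
- Loss needs two missed visits and failed contact attempts (Protocol 5.5).
- Adverse events are to be reported when they occur (Protocol 4.2), and revisions go on the adverse event form (Protocol 8.1).
- SAP 7.6 tabulates deaths, revisions, terminations and the follow-up rate by visit, so a reader will see how much was lost.

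All of that stands, and it may keep loss small. None of it shows what the remaining loss does to the claim. The telephone call is also optional and works only for patients who can be reached.

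The estimator is standard for a single-arm observational study, and the loss rate used here is assumed. Both are fair points. They are reasons to add a supplementary analysis, not to replace the primary one.

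A reader might infer more than the documents support:
- *That any pass at 93–94% falls to a doubling.* At 94% a doubling leaves the lower limit above 90% in the formula, even with 30% lost.
- *That survivorship would really be below 90%.* Losing the claim means only that the lower limit crosses 90%. Moving the point estimate there from 93.0% takes 4.2 to 12.5 times the hazard.
- *That lost hips did fail more often, or that loss was high.* The documents contain no data on either.

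**Conclusion.** The structural point holds in full: the 10-year conclusion depends on non-informative censoring, and no analysis in the SAP can show how much.

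The practical size is conditional. A narrow pass, with an estimate of about 93–93.5%, is fragile to roughly a doubling or less of the revision hazard in lost hips (up to about 2.5 with a linear interval) once 20–30% are lost. With 10% lost, the same band needs 1.8 to 4.4 times. A pass at 95% or above is fairly robust. The proposed analysis would show which case applies.

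These figures rest on 512 independent hips, constant hazard, even loss over time and an assumed loss of 10–30%. The interval type alone moves the multiplier from 1.3 to 1.8 at 93.0% with 20% lost, so the SAP should name it. This should be fixed, but it does not invalidate the primary analysis.

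**What to change.** State the interval type in SAP 7.9 and add:

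> As a sensitivity analysis on the FAS, revision times after loss to follow-up or withdrawal (not death) will be multiply imputed with the revision hazard multiplied by 1, 1.5, 2, 3, 5 and 10, using the same interval type as the primary analysis. The multiplier at which the lower 95% limit falls below 90% at 10 years will be reported beside the primary result, together with the 10-year follow-up rate, and the claim will be worded in the light of it. The analysis will be repeated on all implanted hips (SAF), with multiplier 1 shown for both sets so that population and censoring effects can be separated.

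SAP 6.3 says that the last subject's last visit has taken place, so SAP 7.14 should label this as added after that date. The same section should say why the protocol's multiple imputation was not carried to the primary endpoint. No fixed cut-off for the multiplier is proposed, since any value would be arbitrary.

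The cost is one SAP paragraph and one program on data already collected. The downside is that a narrow pass may have to be reported with a caveat.
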